The MacArthur-Bates Communicative Development Inventories (CDI):⁴⁶ The MacArthur-Bates CDI is the most widely used parent report measure of language development. The CDI includes two versions: Words and Gestures for ages 8-16 months and Words and Sentences for children ages 16-30 months. Scores are reported as percentiles compared to age-standardized norms.

Brief Infant Toddler Social Emotional Assessment (BITSEA):^{43,44,47} The 42-item BITSEA is a parent report measure of social-emotional and behavior problems in children ages 1-3. The Problem Index includes internalizing, externalizing and dysregulation problems. The internalizing scale has items that assess depression, anxiety and negative emotionality.

Gross Motor Function Classification System (GMFCS):^{48,49} The GMFCS is a five level classification system that assess the gross motor function of children with and at risk for cerebral palsy, from infancy through age 12. It differentiates children into one of five levels of functioning, based on the child's current gross motor ability, limitations in function, and need for assistive technology.

Behavior Assessment System for Children – Second Edition Preschool, Parent (BASC-2 Preschool Parent's version):⁵⁰ The BASC-2 PRS-P is a 134 item questionnaire that assesses psychological status and adaptive behavior. The parent/caregiver rates the occurrence of behaviors using a 4-point rating scale. The profile yields eight clinical scales (hyperactivity, aggression, anxiety, depression, somatization, atypicality, withdrawal and attention problems) and four adaptive scales (adaptability, social skills, activities of daily living and functional communication) as well as four composite scores (externalizing problems, internalizing problems, adaptive skills and the Behavioral Symptoms Index).

These neurodevelopmental tools will be evaluated on the following schedule:

12 month follow-up	24 month follow-up
--------------------	--------------------

BSID-III	BSID-III, CDI, BITSEA, GMFS, BASC-2
----------	-------------------------------------

We recognize that neurodevelopmental outcomes may be influenced by other factors that extend beyond early interventions during the neonatal and infant periods. Such factors may include duration of parenteral nutrition, duration of IFER, mean IVFE dose, percent nutrition obtained via the enteral route compared to the parenteral route, type of enteral intake (i.e. breast milk), the development of essential fatty acid deficiency, as well as early intervention programs, attendance at daycare/preschool, and socioeconomic status. As such, we will evaluate study subjects every 6 months (\pm 30 days) and collect the following data, which will be used in final statistical analyses to evaluate predictive variables on neurodevelopmental outcomes:

1. Current parenteral and enteral nutrition parameters
2. Current IVFE dose/mean IVFE dose over course of previous 6 months
3. Essential fatty acid profiles (if available, according to each institution's standard of care), evaluating for development of essential fatty acid deficiency
4. Attendance at early intervention programs and/or daycare/preschool

Monitoring for Adverse Events

The study coordinator and investigators at each site will monitor for adverse reactions. Although generally very well-tolerated, the administration of PN with Intralipid® 20% is associated with a number of adverse events.

Determination of Expectedness:

Adverse events will be classified as expected or unexpected. Expected adverse events include those listed in the clinical protocol, the package insert for PN with Intralipid® 20%, and those events listed in the informed consent document.

These may include, but are not limited to:

1. Line complications including:
 - a. Catheter-related blood stream infection (CRBSI)
 - i. Defined as: A laboratory-confirmed bloodstream infection (LCBI) where central line (CL) or umbilical catheter (UC) was in place for >2 calendar days on the date of event, with day of device placement being Day 1, *and* a CL or UC was in place on the date of event or the day before. If a CL or UC was in place for >2 calendar days and then removed, the LCBI criteria must be fully met on the day of discontinuation or the next day^{51,52}
 - ii. This is in distinction to a catheter-related blood stream infection (CRBSI) whose definition requires removal of the catheter⁵¹
 - b. Need for catheter replacement
2. Hyperglycemia > 300 mg/dL
3. Hypertriglyceridemia >400 mg/dL
4. Development of essential fatty acid deficiency
5. Moderate undernutrition (decreased in z-score by ≥ 2 standard deviations) to severe undernutrition (decreased in z-score by ≥ 3 standard deviations)
6. Thrombophlebitis
7. Hypercoagulopathy
8. Thrombocytopenia (platelet count <50 k/mm³)

Determination of Relatedness:

Generally, the definition of an adverse event could include worsening of a pre-existing condition and investigators could be asked to make the distinction between exacerbation of a pre-existing condition and an event related to the study protocol when recording and reporting adverse event. However, due to the nature of the population being studied, the typical effects of the underlying condition may not yet be present at Baseline.

Standard IV lipid dosing compared to IV lipid minimization for the prevention of PNAC/PNALD

Based on clinical information, an adverse event will be determined by the site PI to be definitely not related, unlikely to be related, possibly related, definitely related or insufficient information to Intralipid® 20% administration or other study procedures. Usual effects from the subject's condition that are considered by the site PI to be not related to Intralipid® 20% administration or other study procedures will be noted in the subjects' medical records but will not be recorded or reported as an adverse event for this study. Examples include emesis, reflux and pain due to an expected surgery/procedure.

Adverse Event Reporting

All adverse events that occur from the time of consent until the patient completes 12 weeks of TPN or has been off TPN for 7 days, whichever comes first will be assessed for expectedness and relatedness and recorded in the subject's study binder.

Only adverse events considered to be possibly related to Intralipid® 20% administration or other study procedures will be reported to the sponsor, the IRB, the FDA, and the DSMB.

Severe Adverse Event Reporting

Although no serious adverse reactions are anticipated, study participants will be monitored, and any such events will be recorded and reported to the appropriate regulatory committees. These include:

- Death while on the study
- Any study-related event that prolongs hospitalization
- Any study-related event that requires an operative procedure

Mortality will be defined as a death occurring at any time during the child's admission to the hospital. The cause of death, autopsy findings and whether the subject was on study drug at the time of death will also be recorded.

All adverse events will be graded as follows in their relation to IFER: definitely not related, unlikely to be related, possibly related, definitely related or insufficient information. All cases rated as possibly or definitely related will be defined as an SAE. These SAEs will be reported to the University of Michigan Sponsor-Investigator within 48 hours. The site PI will be contacted immediately and the case will be evaluated for reporting to IRB, FDA and study termination, if deemed necessary. Each clinical site will report SAEs to their local IRB as per their standard reporting policy. As per 21 CFR 312.32(c), the sponsors will also notify FDA and all participating investigators in an IND safety report of any adverse experience associated with the use of the drug that is both serious and unexpected.

Data Safety Monitoring Board

An independent data safety monitoring committee will be established to monitor the study for safety and to determine if a statistical difference has been achieved between the two groups for the primary outcome measure at interim data analyses. The data safety monitoring committee will review the data at the halfway point of the study to assess the safety and efficacy of the study to that point. If safety issues are revealed the study investigators and each site's IRB will be notified immediately. The data safety monitoring committee will also ensure that adverse events are promptly reported to the FDA, and all participating investigators will be notified as well of any adverse experience associated with the use of the drug that is both serious and unexpected.

Sample Size Determination

The sample size was calculated for the primary outcome (rate of rise of direct bilirubin) using previously published data as well as our clinical experience.^{22,23} We have assumed that the mean bilirubin levels at baseline, 4 weeks, 8 weeks and 12 weeks in the standard dosing group (2-3 g/kg/day) will be 0.55 mg/dL, 1 mg/dL, 1.5 mg/dL and 2 mg/dL corresponding to a slope of 0.125 mg/dL/week over 12 weeks. The standard deviation of the bilirubin measures at each of these four time points is 1. Likewise, we have estimated that the mean bilirubin levels at baseline, 4 weeks, 8 weeks and 12 weeks in the minimization group (1 g/kg/day) will be 0.45 mg/dL, 0.5 mg/dL, 0.45 mg/dL and 0.5 mg/dL (a slope of roughly zero). The standard deviation of the bilirubin measurements at

each of these four time points is 1. The correlation of any two adjacent measures on the same individual is 0.5. This correlation drops to 0.354 between baseline and 8 weeks and to 0.25 between baseline and 12 weeks.

Using the above assumptions, a sample size of 15 subjects per group using a repeated measures ANOVA will have 85% power to detect the change in slopes as being significant at the 0.05 level, 79% power to detect a difference in means overall between groups and 88% power to detect the general change in means over time across the two groups. When the sample size is increased to 20 subjects per group, the above power numbers increase to 95%, 90% and 96%, respectively. If 30 subjects are recruited per group this design will allow for a 33% attrition rate by twelve weeks as we expect that not all patients will require PN for the full 12 weeks of the initial study period. Thus, we will recruit a minimum of 30 subjects per group to ensure adequate power to detect our primary outcome measure.

Of the secondary outcomes, sample size was also calculated for the incidence of cholestasis. Assuming an incidence of 50% in the standard group and an incidence of 10% in the minimization group, with $\alpha = 0.05$ and power of 80%, a sample size of 23 is required for each group. Regarding the other secondary outcomes, our sample size is large enough to allow for establishing trends which may then highlight avenues for future research.

Planned Statistical Analysis

All data analysis will be directed and performed by a statistician through the Center for Statistical Consultation and Research at the University of Michigan (<http://cscar.research.umich.edu/about/>). Data will be analyzed using SAS software release 9.3 for Windows (Copyright, SAS Institute Inc., SAS and all other SAS Institute Inc. product of service names are registered trademarks or trademarks of SAS Institute Inc., Cary, NC, USA). All study subjects will be included in the statistical analysis in an intent-to-treat manner.

Descriptive statistics using standard statistical tests (e.g. Student's t-test, paired sample t-test, Wilcoxon rank sums tests, Fisher's exact tests, Chi-square test, McNemar's test, etc.) will be used throughout the statistical analysis of data. Logistic regression will be used to compare differences between groups. Because septicemia can exacerbate PNAC, we will include the incidence of septicemia as a covariate in our analysis. Septic episodes will be defined as positive cultures or clinical presentation consistent with sepsis during the 7 day period corresponding to the subject's weekly bilirubin value. The number of septic episodes will be accounted for using a Poisson regression analysis (or possibly a negative binomial regression if there is more variability than expected for a Poisson distribution), with the total time on PN as an offset, allowing us to compare the rate of occurrence of septic episodes in the two groups.

Primary Outcome Measure

The primary outcome measure – change in direct bilirubin as a function of time (mg/dL/week) between the two groups – will be evaluated using a linear mixed model analysis to compare the slope of total bilirubin levels between the standard and reduced groups. This model will allow us to examine the degree of variability between subjects in the rate of change over time, and will take this variability into account in the model by including a random effect for the slope of time for each subject as well as a random intercept for each subject.

Secondary Outcome Measures

1. Time to PNAC (direct bilirubin ≥ 2 mg/dL) and time to severe PNAC (direct bilirubin ≥ 4 mg/dL)

The time to development of a first occurrence of PNAC and of severe PNAC will be evaluated using survival analysis. Initially, we will compare the two groups using Kaplan-Meier curves, but the eventual analysis will take into account important covariates, such as development of sepsis, average IVFE dose and percentage of calories from enteral feeds using a Cox proportional hazards survival analysis. We will test whether the proportional hazards assumption is met for the analysis by including an interaction term between treatment group and time to see if any differences between the groups are consistent or increase/decrease over time. The effect of important time-varying covariates (e.g., septic episodes) can also be taken into account using a Cox model.

2. Level of peak total and direct bilirubin

These measures will be compared between the two treatment groups using a linear mixed model.

3. Incidence of PNAC, severe PNAC, and EFAD

The number of occurrences of each of these outcomes will be compared using either a Poisson regression model or a negative binomial model if the variance in these counts is greater than expected for a Poisson distribution. We will also include the time on TPN as an offset, so that we can compare the rates of occurrence of each of these outcomes for the two treatment groups. These regression models will be adjusted for the covariates such as development of sepsis, average IVFE dose, and percentage of enteral feeds.

4. Adequacy of growth as evaluated by z-scores for weight, height and head circumference

The z-scores for each of these measures will be compared between the two treatment groups using a linear mixed model. For normally growing infants, we would expect that there would not be a trend in z-scores because we would expect them to maintain their curve. However, for the subjects in this study, there may be a loss in z-score over time due to inadequate growth. The slopes of the changes in these z-scores over time will be compared between the two treatment arms. A random intercept will be included for each subject to allow for individual variability in average values as well as a random slope to allow for variability in the rate of change over time across subjects. Important covariates, such as gestational age (<32 weeks gestation vs. ≥32 weeks gestation) and birth weight will also be used as covariates in this analysis.

5. Neurodevelopmental Outcomes

Bayley Scales of Infant and Toddler Development (BSID-III):⁴⁵ Raw scores are converted to composite and subscale scores using age-standardized norms. Scale composite average internal consistency reliability coefficients range from .91 to .93 with subtest reliability ranging from .86 to .91. Validity-related studies indicate relatively high correlations (.72-.79) with the Wechsler Preschool and Primary Scale of Intelligence – Third Edition (WPPSI-III)⁵³ and with the Preschool Language Scale – Fourth Edition (PLS-4)(.71-.83).⁵⁴

The MacArthur-Bates Communicative Development Inventories (CDI):⁴⁶ The MacArthur-Bates CDI is the most widely used parent report measure of language development. The CDI includes two versions: Words and Gestures (ages 8-16 months) and Words and Sentences (ages 16-30 months). Scores are reported as percentiles compared to age-standardized norms.

Brief Infant Toddler Social Emotional Assessment (BITSEA):^{44,47,55} Dichotomous scores are generated based on cut-off scores, which identify subjects to be at risk. Internal consistency coefficients range from .80 to .82. Test-retest reliability is acceptable at .80-.85. Recent evidence identifies the BITSEA as the best short tool for early detection of psychosocial problems in two-year olds.⁴⁰

Gross Motor Function Classification System (GMFCS):^{48,56} Interrater reliability is 0.75 and both content and predictive validity are well-demonstrated in child and adult populations.⁵⁶⁻⁵⁸

Behavior Assessment System for Children – Second Edition Preschool, Parent Preschool Parent’s version (BASC-2 PRS-P):⁵⁰ Limited construct validation data indicate strong correlations with similar scale scores. Primary measurements from the BASC-2 including the Adaptive Behavior Composite and the Behavior Symptoms Index will be reported as T-scores and as percentiles. Secondary analyses will be conducted on the subscales.

For the comparison of the two treatment arms across time for neurological measures that are approximately continuous, a linear mixed model will be used with a repeated measures covariance structure. The best covariance structure will be chosen based on a comparison of the Akaike Information Criterion (AIC) and Bayes Information Criterion (BIC). This will allow us to adjust for correlated measures within a subject and possibly for unequal variances across times points and across groups. Each measure will be compared between the groups at each time point, controlling for important demographic variables, such as gestational age, diagnosis, bilirubin (total and direct), as well as a time-varying covariate for development of essential fatty acid deficiency. Importantly, we will also evaluate the influence of three IFER-related variables on neurodevelopmental

Standard IV lipid dosing compared to IV lipid minimization for the prevention of PNAC/PNALD

outcomes: mean IVFE dose, duration of IFER and the development of essential fatty acid deficiency. Since total and direct bilirubin are expected to be highly collinear, we will use only one of these predictors and compare the models using AIC and BIC to decide which is a better predictor of the particular outcome being assessed.

A logistic regression with Generalized Estimating Equations (GEE) approach will be used to compare the binary outcomes between groups.

Intent to Treat

All statistical analyses will be performed using an intent to treat approach.

Potential Confounding Variables:

Nutritional intake: Differences in nutritional intake alter the risk of PNAC as any amount of enteral nutrition has been shown to enhance rehabilitation.⁵⁹ Infants able to tolerate even trophic amounts of enteral calories will be at decreased risk compared to those than those who are completely PN-dependent. Every attempt will be made to standardize enteral feeding advancement. This will be possible because of the relatively homogeneous nature of the subjects enrolled and their similar expected ability to tolerate enteral feeds. Statistical analyses will account for variations in enteral intake. Overfeeding may result in hepatic steatosis that can also worsen PNAC, therefore all subjects will follow a strict guideline for PN administration. Additionally, the administration of breast milk, which contains proteins necessary for optimal brain development, may be a confounding variable and will be accounted for in the final data analysis. PN duration (with or without IFER) may also affect neurodevelopmental outcomes and will be included as a covariate in the statistical analysis.

Variation in IVFE dose: The IVFE dose may vary depending on the clinical status of the subject (e.g. elevated TG, EFAD, direct bilirubin ≥ 2.5 mg/dL, nutritional and/or fluid status). Every attempt will be made to maintain dosing within the assigned treatment arm. Based on previous experience using IFER at the University of Michigan, hypertriglyceridemia and EFAD are exceedingly rare occurrences, therefore, the IVFE dose is not expected to be adjusted frequently based on these findings. Statistical analysis will account for differences in IVFE dose by using the mean IVFE dose as well as the duration of IVFE/IFER as a covariate.

Critical medical incidences: As differences in the degree of medical illness between groups may adversely affect the development of PNAC, a number of complications will be examined as secondary outcome measures including sepsis and mortality rates as well as days in the neonatal intensive care unit.

Occurrence of sepsis: Because sepsis may lead to increased levels of direct bilirubin and may worsen PNAC, the occurrence of sepsis is being recorded and a marker of morbidity.

References

2. Merritt RJ. Cholestasis associated with total parenteral nutrition. *J Pediatr Gastroenterol Nutr*. 1986;5(1):9–22.
6. Kelly DA. Liver complications of pediatric parenteral nutrition--epidemiology. *Nutrition*. 1998;14(1):153–157.
9. Kelly DA. Intestinal failure-associated liver disease: what do we know today? *Gastroenterology*. 2006;130(2 Suppl 1):S70–7. doi:10.1053/j.gastro.2005.10.066.

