IVFE reduction (IFER) during the administration of neonatal parenteral nutrition will lead to a significant decrease in the rate of rise of direct bilirubin (mg/dL/week) when compared to standard therapy.

Secondary Hypotheses

1. The time to development of PNAC, when present, will be longer with IFER when compared to standard IVFE therapy.
2. IFER will not be associated with a significant increase in failure to thrive (as assessed by growth parameters) or the development of essential fatty acid deficiency (EFAD) when compared to standard IVFE therapy.
3. Neurodevelopmental outcomes (NDOs), when assessed at 12 and 24 months of corrected gestational age, will be similar for those treated with IFER and standard IVFE therapy.

Specific Aims

1. To determine whether neonates and infants receiving PN with IFER (1 g/kg/day) will have lower rates of rise of direct bilirubin compared to those receiving standard IVFE therapy (3 g/kg/day)
2. To compare the time to development of PNAC in neonates and infants receiving PN with IFER (1 g/kg/day) compared to those receiving PN with standard IVFE administration (3 g/kg/day)
3. To determine if IFER results in normal growth and essential fatty acid (EFA) parameters by measuring weight, length, head circumference (weekly) and EFA profiles (every 2 weeks in the IFER group) during the treatment period.
4. To compare NDOs at 12 and 24 months of corrected gestational (± 2 weeks) age of those treated with IFER with those treated with standard IVFE doses using a combination of neurodevelopmental screening tools (e.g. Bayley Scales of Infant Development, MacArthur Communicative Development Inventory, etc.) aimed at capturing several developmental domains such as motor, cognition, speech and language, sensory, and behavior.

Study Definitions

Subjects will be considered “on treatment” from the time of randomization until 7 days after PN has been discontinued, but not to exceed a total of 84 days. Subjects will be considered “on study” until they complete their neurodevelopmental testing at 24 months corrected gestational age (± 2 weeks).

Study Design

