This is a multi-institution, prospective, randomized study evaluating IVFE dose reduction on the development of PNAC as a proxy measure of PNALD in neonates requiring prolonged PN. The definition of PNAC will be that used predominantly in the literature – a direct bilirubin level of ≥ 2 mg/dL, documented on two occasions 1 week apart, in patients who have required parenteral nutrition for more than 2 weeks. **Eligible neonates will be randomized into two treatment arms: standard IVFE administration (3 g/kg/day) or IVFE reduction (IFER) (1 g/kg/day).** A total of 60 subjects (30 subjects per arm) will be included in the study. The study will evaluate

short- and long-term outcomes of this strategy. In the short-term, infants will be followed for up to 12 weeks for the development of PNAC. If a subject's PN is discontinued before 12 weeks, and if they remain in the hospital, follow-up data will be collected for an additional 7 days but not beyond a total of 84 days. Only standard-of-care data will be collected during these 7 days. No procedures will be performed for the purpose of this study during these 7 days. In the long-term, subjects' neurodevelopmental outcomes will be assessed at 12 and 24 months corrected gestational age (± 2 weeks).

Primary outcome measure:

1. The rate of rise of direct bilirubin as a function of time (mg/dL/week) between the two groups over 12 weeks or until the subject has been off of PN for >7 days, whichever comes first.

Secondary outcome measures

1. Initial 12 week period:
 - a. The incidence of PNAC (direct bilirubin ≥ 2 mg/dL) and severe PNAC (direct bilirubin ≥ 4 mg/dL in subjects on parenteral nutrition for at least 2 weeks)
 - b. The time to development of PNAC and severe PNAC
 - c. The peak total and direct bilirubin levels
 - d. The incidence of EFAD
 - e. Adequacy of growth as evaluated by z-scores for weight, height, and head circumference
 - f. Other safety measures assessed during the initial 12 week period will include adverse events (e.g., episodes of sepsis and catheter-related blood stream infections).
2. Long-term follow-up:

Neurodevelopmental assessments will include:

 - a. At 12 months corrected gestational age (± 2 weeks):
 - i. Bayley Scales for Infant and Toddler Development (BSID-III)
 - b. At 24 months corrected gestational age (± 2 weeks):
 - i. Bayley Scales for Infant and Toddler Development (BSID-III)
 - ii. MacArthur-Bates Communicative Development Inventories (CDI)

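### Secondary hypotheses 2 and 3 state no harm, but the plan only tests for a difference and sets no margin or interval rule, so a non-significant result would not rule out meaningful harm

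*Combined protocol and SAP*

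**What the plan says.** Under Secondary Hypotheses, item 2 reads "IFER will not be associated with a significant increase in failure to thrive (as assessed by growth parameters", and the sentence goes on to include EFAD. Item 3 says that neurodevelopmental outcomes at 12 and 24 months corrected age "will be similar for those treated with IFER and standard IVFE therapy".

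The analyses are under Planned Statistical Analysis, Secondary Outcome Measures:

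- **Growth:** a linear mixed model comparing the slopes of the z-scores.
- **EFAD:** Poisson or negative binomial regression.
- **Neurodevelopment:** a mixed model for continuous measures, in which "Each measure will be compared between the groups at each time point", and logistic regression with GEE for binary measures.

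No equivalence or non-inferiority margin appears anywhere, nor any rule on what interval would support either hypothesis.

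On size, Study Design says "A total of 60 subjects (30 subjects per arm) will be included in the study". Sample Size Determination ties that number to the bilirubin slope: "Thus, we will recruit a minimum of 30 subjects per group to ensure adequate power to detect our primary outcome measure". It adds a calculation for the incidence of cholestasis. Of the remaining secondary outcomes it says only that "our sample size is large enough to allow for establishing trends which may then highlight avenues for future research".

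**The concern.** Both hypotheses assert the absence of harm, but the planned tests can only find a difference. Failing to find one is not evidence that there is none, and failure becomes more likely as fewer infants are followed. Hypothesis 2 goes further, because on its wording non-significance is the success condition.

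The background section gives growth, EFAD and neurodevelopment as reasons for the trial, and it lists small sample size among the limits of the earlier neurodevelopmental pilot. It also cites a randomized pilot in which weight z-scores rose more on standard dosing (p=0.006), so an effect on growth is a live possibility. At stake is whether an imprecise null result on these outcomes may be counted as support for safety.

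**Working it through.** **1. The plan's own figures.** No figure is stated for growth, EFAD or neurodevelopment. The stated figures concern other outcomes, and they reproduce. With the plan's means, SD 1 and correlations, at two-sided 0.05, a repeated measures ANOVA (Greenhouse-Geisser, Muller-Barton approximation) gives the following power for slopes, group means and time:

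| Per group | Stated | Recomputed |
|---|---|---|
| 15 | 85%, 79%, 88% | 86.1%, 79.6%, 88.9% |
| 20 | 95%, 90%, 96% | 95.1%, 90.2%, 96.5% |

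Direct simulation is slightly lower for slopes (83% and 93%). For cholestasis at 50% vs 10%, Fisher's exact test first passes 80% power at 23 per group (81.1%), as stated. The sizing is in order for what it covers, but it does not cover hypotheses 2 and 3.

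**2. Inputs for hypotheses 2 and 3.**

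- n = 30 per arm, from Study Design.
- n = 20 per arm as a scenario, from 30 × (1 − 0.33) ≈ 20. The plan says "this design will allow for a 33% attrition rate by twelve weeks", but that refers to infants who no longer need parenteral nutrition. No attrition figure is given for 12 or 24 months, so 20 per arm at follow-up is an assumption.
- Alpha 0.05. The plan gives this level for the primary outcome ("to detect the change in slopes as being significant at the 0.05 level") without stating sidedness. Two-sided is assumed.
- Results are in SD units, because no SD is given for these outcomes.

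**3. Precision for one unadjusted continuous outcome.** The 95% half-width is t(0.975, 2n−2) × √(2/n).

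- n = 30: 2.002 × 0.2582 = 0.52 SD
- n = 20: 2.024 × 0.3162 = 0.64 SD

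If a composite score has SD 15 (an assumption), these are 7.8 and 9.6 points. An observed deficit of 0.50 SD with 30 per arm would have an interval from a 1.02 SD deficit to a 0.02 SD advantage. It would be non-significant, and on hypothesis 2's wording it would count as confirmation.

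**4. Chance of non-significance under real harm.** Non-central t with noncentrality d × √(n/2):

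| True deficit | n = 30 | n = 20 |
|---|---|---|
| 0.5 SD | 1.936, giving 52% | 1.581, giving 66% |
| 0.33 SD | 1.278, giving 76% | 1.044, giving 83% |

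**5. A binary illustration.** Assume growth-failure rates of 10% vs 30%; neither rate is in the documents. Full enumeration of Fisher's exact test gives non-significance 63% of the time with 30 per arm and 76% with 20. This is not the planned growth analysis, which is a mixed model of z-score slopes.

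**6. EFAD.** With no events in n infants, the one-sided 95% upper limit is 1 − 0.05^(1/n), which is 9.5% for n = 30 and 13.9% for n = 20. Even a clean arm leaves an appreciable rate open. The comparison is also uneven: the laboratory table under Data Collection schedules fatty acid profiles every 2 weeks in the reduced-dose arm, but in the standard arm only once lipid is restricted.

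**7. What a margin would demand.** For non-inferiority with true difference 0, one-sided 0.025 and 80% power, n per arm = 2(1.960 + 0.842)²/m² ≈ 15.70/m². The margins are assumed.

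| Margin | n per arm needed | Power at 30 (20) per arm |
|---|---|---|
| 1/3 SD | 142 | 25% (18%) |
| 0.5 SD | 63 | 49% (35%) |
| 0.75 SD | 28 | 83% (66%) |

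**The case against.** The strongest reply is that the plan never says that p > 0.05 establishes similarity. Hypothesis 3 mentions no significance test. The aims are largely neutral: compare neurodevelopment, determine whether growth is normal. The sample size section claims only trends. All of this is correct. Only hypothesis 2 is literally met by non-significance, and how the results would be reported is an inference. But the trends sentence does not withdraw the two hypotheses; it concedes that the trial cannot support them.

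A reader might infer that the trial would probably report no harm whether or not harm exists. The documents do not support that. At 0.5 SD and 30 per arm, non-significance on one outcome is close to a coin flip, and hypothesis 3 covers three Bayley scales at two visits plus four further instruments, with no multiplicity correction stated. With a uniform 0.5 SD deficit and assumed correlations of 0.5 to 0.7, simulation gives all six Bayley comparisons non-significant in only about 15% to 24% of trials with 30 per arm. A smaller deficit, or one confined to a single domain, would be missed more often.

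It is also fair that weekly measurements and covariates could narrow the intervals, and that the unadjusted figures above do not model the planned mixed models. Neither supplies the missing decision rule.

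**Conclusion.** The concern holds for individual outcomes. Hypothesis 2 makes non-significance its success condition, hypothesis 3 asserts similarity, and nothing in the analysis plan says what evidence would support either. At full enrolment, an unadjusted comparison carries an uncertainty of about half an SD either way and misses a true 0.5 SD deficit 52% of the time. The corresponding figures of 0.64 SD and 66% hold only if follow-up falls to 20 per arm. The 10% vs 30% growth-failure rates, the SD of 15, the margins and the correlations are assumptions.

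The point concerns what may be concluded from secondary outcomes. It does not touch the primary bilirubin comparison, and it does not show that a false all-clear across all outcomes is likely.

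**What to change.** Bring Secondary Hypotheses 2 and 3 into line with the trends statement in Sample Size Determination:

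1. Reword both as estimation: the difference between arms in growth, EFAD and neurodevelopment will be estimated and reported with its 95% confidence interval.
2. Add one sentence under Planned Statistical Analysis: for these outcomes, p > 0.05 is not evidence of similarity or of no increase.
3. If the sponsor wishes to keep a claim of similarity or no increase, restrict it to one or two key outcomes, for example a Bayley composite or the weight z-score slope. Allow it only if the interval excludes a margin that is justified and fixed in a dated amendment before any outcome data by arm are examined. Otherwise report the result as inconclusive. Setting the margin merely before unblinding would be a weak safeguard, because the Blinding section leaves investigators and the inpatient team unblinded.

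Items 1 and 2 change wording only. Item 3 needs a clinical justification for each margin, which is why it should be limited to a few outcomes. The cost is in the conclusion: at this sample size the likely result becomes inconclusive instead of similar.
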